7.2 SECONDARY EFFICACY ANALYSIS

7.2.1 Proportion of Survivors at Study Days 28 and 91

The effect of ELAD on the proportion of subjects who survived at End of Study Days 28 and 91 will be estimated with 95% confidence intervals for the ITT, mITT, PP and Safety population. Analyses will be presented using the last date known alive, leaving subjects who are not known to be dead, in both the numerator and the denominator. Additional analysis will be done for subjects whose Study Day 28 and/or 91 survival status is unknown at the time of database lock. These subjects will not be included in either the numerator or the denominator of the calculation.

7.2.2 Early Change in Bilirubin Level (ECBL) at Study Day 7

There is a strong correlation between ECBL and response to therapy, as demonstrated by the prior studies evaluating the effects of corticosteroids in AH (Mathurin et al. 2003). Post-hoc analysis of the VTI-208 Safety population suggested that there were more ECBL20 Yes subjects in the ELAD-treated group, and the survival of ECBL20 Yes subjects was significantly higher than the survival in ECBL20 No subjects.

A secondary endpoint for the VTL-308 study will be the proportion of subjects who achieve ECBL20 at Study Day 7 in the ITT population. The 20% or greater threshold for the reduction in ECBL, and the 7-day time point, were chosen as this is consistent with prior literature (Lee et al. 2014, Li et al. 2016, López-Velázquez et al. 2014, Louvet et al. 2007, Mathurin et al. 2003, Morris and Forrest 2005) and in the findings from the VTI-208 study. Differences between treatment groups will be analyzed using a Chi-squared test. The same analysis will also be carried out on the safety population as an exploratory sensitivity analysis.

Definition of Early Change in (total) Bilirubin (tBili) Level (ECBL)

Subjects who died within 7 days (including Day 7) will be excluded from the analysis. ECBL (End point minus start point) will be expressed as a percentage of start point.

- For the start point value, “Within 6 hours prior to ELAD start” tBili value and “Day 2” tBili value will be used for ELAD-treated subjects and Control subjects, respectively;
- For the end point value, “Day 7” tBili value (if the subject was not on treatment when the lab test took place and the value was collected greater than 6 hours after treatment ended) will be used for ELAD-treated subjects. If the value was collected within 6 hours of treatment ending, use “24 hours Post-ELAD Stop” tBili value. “Day 7” tBili value will be used for Control subjects.

Missing Data for Calculations of ECBL

- For the start point value, if End of Study Day Results were used, then start point should be the corresponding Study Day value. Otherwise, if the value is truly missing, Last Observation Carried Forward (LOCF) will be used for both ELAD-treated and Control subjects;
- For the end point value, if End of Study Day Results were used, then end point should be the corresponding Study Day value. Otherwise, if the value is truly missing, “24 hours Post-ELAD Stop” tBili value will be used, and if “24 hours Post-ELAD Stop” tBili value is not available, LOCF will be used.

There are three sets of tBili measurements collected on the CRF (MELD tBili – used to calculate MELD scores at various times during the study; lab tBili – measurements taken as part of laboratory analyses collected at various times during the study; and MADD tBili – used to calculate Maddrey scores at various times during the study). MELD tBili should be prioritized over lab tBili and MADD tBili. If MELD tBili is missing then use lab tBili then MADD tBili.

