7.3 PRIMARY EFFICACY ANALYSIS

7.3.1 Overall Survival (OS) of AILD Subjects through at Least Study Day 91

OS will be assessed using a Kaplan-Meier survival analysis of the intent-to-treat (ITT) population utilizing a log-rank test, with follow-up Protocol VTL-308E providing additional survival data up to a maximum of 5 years that will be included, as available, through VTL-308

study termination. Model-based estimates and confidence limits will be calculated for median survival by treatment group and the hazard ratio and its confidence limits. This analysis will also be carried out on the mITT, Per-Protocol (PP) and Safety populations as sensitivity analyses. Two-tailed alpha for the log-rank test will be set at 0.05. The statistical analysis plan will outline the methods used to account for missing data in this and all other analyses.

The statistical analysis plan will also evaluate differences in standard of care between the groups that may affect subject outcome, such as differences in the administration of steroid therapy, and define analytical strategies to deal with those differences should they arise.

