4 STUDY POPULATION PARAMETERS

4.1 DISPOSITION

VTI-308 End of Study Disposition and VTL-308E Disposition at time of cut-off of all subjects will be presented in a table by treatment group for ITT population. These presentations will include the number of subjects who completed their Study Day 91 visit and the number who discontinued, as well as the reason for study discontinuation. The disposition for subjects who entered VTL-308E when the database locks will also be provided. Survival status at time of Day 91, Day 180, Day 365 and time of cut-off will be summarized using ITT populations. Additionally, subjects who received a liver transplant and/or were diagnosed with cancer will be summarized using the ITT population.

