7 EFFICACY ANALYSIS

Unless otherwise specified, all analyses will be of randomized subjects by treatment group.

No data imputation will be used, except for the ECBL and Lille analyses. For the primary log-rank analyses of the effect of ELAD on OS, the subject's last available study evaluation through Day 91 after the calendar date at which the last subject was randomized will be used. This OS follow-up will draw from data generated by VTL-308 and VTL-308E follow-up data. Every effort will be made to capture the survival status of each randomized subject through Day 91 after the calendar date at which the last subject was randomized.

For the log-rank analysis of the effect of ELAD on OS, the null hypothesis will be that the true survival curves do not differ and will be tested at the two-sided 0.05 level of significance. The primary efficacy analysis will be carried out on the ITT population, and sensitivity analyses will be performed using the mITT, PP and Safety populations. Kaplan-Meier estimates of survival will be generated for both treatment groups, and estimates will be obtained for median survival, 25th and 75th quartiles. A Cox regression analysis will be performed to obtain an estimate of the hazard ratio and corresponding confidence limits. Exploratory analyses of treatment effect within subgroups will be performed.

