7.1 PRIMARY EFFICACY ANALYSIS

7.1.1 Overall Survival (OS) of Subjects with sAH through at least Study Day 91

OS will be assessed using a log-rank analysis of survival data in the intent-to-treat (ITT) population. Protocol VTL-308E will provide additional survival data up to a maximum of 5 years. Kaplan-Meier estimates of survival will be provided, along with estimates of median survival, 25th and 75th quartiles, by treatment group, while a Cox regression analysis will be used to provide estimates of the hazard ratio and its confidence limits. These analyses will also be carried out on the mITT, Per-Protocol (PP) and Safety populations as sensitivity analyses.

In addition, a similar sensitivity analysis for 91-day overall survival will be carried out using overall survival data through Day 91. Subjects who survived at Day 91 are censored at Day 91. Subjects who were lost to follow-up prior to Day 91 are censored at their last contact Study Day.

Although every effort will be made to determine each subject's survival status through the calendar date for the primary analysis of OS, it is possible that some subjects will be lost to follow-up. In the primary OS analysis, such observations will be censored as of the last date when the subject's survival status was known.

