Post-randomization is defined as the steroid starting within one day after Randomization. If start dates are partial/missing for steroid use, the following imputation will be followed:

- If the entire set of steroid dates are partial, and only the year and month are reported, and they are the same year and month as the Randomization date, then the day will be imputed to be the same as the randomization day. If the first steroid date is a complete start date, and the following steroid records have partial dates that are in the same month and year, then all subsequent partial dates will be imputed to be the same as the first steroid date. Otherwise, the day will be imputed to the first day of the month;
- If the entire set of steroid dates are partial, and only the year is reported, and it is the same year as the randomization date, then the day and month will be imputed to be the same as the randomization day and month. If the first steroid date is a complete start date, and the following steroid records have partial dates in the same year, then all subsequent partial dates will be imputed to be the same as the first steroid date. Otherwise, the day and month will be imputed to January 1st;
- If the entire set of steroid dates are completely missing, then the start dates will be imputed to be the same as the randomization date.

The same logic will be applied for steroid end dates, using discontinuation dates instead of randomization dates. If the steroid is ongoing, the last visit date for the subject will be used.

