7.3.6 Selected Labs and MELD Scores Summarized by Visit

Changes in selected lab values and disease severity scores that have been demonstrated to correlate with survival will be presented for the ITT population. Differences between treatment groups at each time point will be analyzed based on a mixed model repeated measure (MMRM) with fixed effects of treatment group, visit and the treatment group by visit interaction, and a covariate of baseline value for the corresponding treatment. An unstructured covariance matrix will be used. If the model does not converge with an unstructured covariance matrix due to insufficient data at some visits, the spatial power covariance structure will be used. In addition, one sample t-test will be used to test if change from baseline value is zero at each time point within treatment group. All changes will be calculated relative to randomization date/time (as all subjects are on standard of care treatment as of the randomization date/time). Additional summaries of changes relative to ELAD start date/time will be provided for selected analyses. For comparative purpose, the Control group will be summarized by changes relative to End of Study Day 2, as this most closely mimics the time of initiation of ELAD treatment in those subjects randomized to ELAD. If Study Day 2 is missing for Control subjects, the last non-missing visit before Study Day 2 will be used for analysis.

As a sensitivity analysis, the analyses will be repeated after the missing data is imputed using the last observation carried forward (LOCF) approach. These will include:

- MELD;
- Total Bilirubin;
- Creatinine;
- INR;
- Sodium.

The values for MELD, Total Bilirubin, Creatinine, INR and Sodium will be displayed in a listing.

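### Day-28 and Day-91 survival proportions count unknown status as alive or drop it; no planned version tests whether unequal or informative loss would change the result (minor, secondary endpoint)

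*SAP*

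**What the plan says.** SAP 7.2.1 gives the rule for the secondary survival proportions at Days 28 and 91. The first presentation uses the last date known alive, "leaving subjects who are not known to be dead, in both the numerator and the denominator". An additional analysis covers subjects whose status is unknown at database lock: "These subjects will not be included in either the numerator or the denominator of the calculation". Neither document plans a version that counts unknown as dead, or a tipping-point analysis. Protocol 7.4.1 names a two-sided 0.05 chi-square test for Day 91. SAP 1.2.2 and 6.1 name it for both days.

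Three other places bear on this:

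- Protocol 7.3.1 passes the question on: "The statistical analysis plan will outline the methods used to account for missing data in this and all other analyses".
- SAP 7 states: "No data imputation will be used, except for the ECBL and Lille analyses". The counting rule in 7.2.1 is not among those exceptions.
- SAP 7.1.1 plans a separate time-to-event analysis to Day 91: "Subjects who were lost to follow-up prior to Day 91 are censored at their last contact Study Day".

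**The concern.** A subject last seen alive on Day 10 and never traced would enter the first table as a Day-91 survivor. That assigns a value to a missing outcome, and the assigned value is always the favourable one. The additional analysis drops the same subject but keeps those who died under observation, so it tends to understate survival.

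The trial is open-label, and SAP 7.1.4 itself allows that care and behaviour after treatment may differ by assigned group. Subjects who disappear therefore need not be balanced between arms or alike in outcome. If they are not, the two planned tables can agree and look robust although a less favourable assumption would change the reading. These are named secondary endpoints of a pivotal trial, and a stress test carries most weight if it is fixed before results are seen.

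**Working it through.** **Inputs.** Protocol 7.1: Control hazard 0.004 per day, hazard ratio 0.4, so ELAD 0.0016; 75 per arm. SAP 1.3: one-year Control survival 40% to 48%, hazard ratio 0.4, missing data 0% to 10%. Neither document gives a target or power for these proportions, so there is no plan figure to reproduce. The inputs do check: ln 2/0.004 = 173 and ln 2/0.0016 = 433 days (protocol about 175 and 438); 0.40^0.4 = 69.3% and 0.48^0.4 = 74.6% (SAP 69.5% and 74.5%).

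**Assumptions.** Exponential survival. A fraction p of each arm is lost, uniformly over Days 0 to 91 and independently of outcome. The SAP's 0% to 10% is a sample-size input, so p is varied.

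**Formulas.** For day T and hazard λ: S = exp(−λT), q = pT/91, and m = (1−S)/(λT), the chance of being alive when lost.

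- Unknown = alive: (1−q)S + qm
- Complete case: (1−q)S/(1−qm)
- Unknown = dead: (1−q)S

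**Day 91, p = 0.10, protocol hazards.**

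- ELAD: S = 0.8645, m = 0.9306, giving 0.871 / 0.858 / 0.778.
- Control: S = 0.6949, m = 0.8382, giving 0.709 / 0.683 / 0.625.

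Differences (ELAD minus Control, percentage points):

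| Scenario | True | Unknown = alive | Complete case | Unknown = dead |
|---|---|---|---|---|
| Day 91, protocol hazards, 2% loss | 17.0 | 16.8 | 17.1 | 16.6 |
| Day 91, protocol hazards, 5% loss | 17.0 | 16.6 | 17.2 | 16.1 |
| Day 91, protocol hazards, 10% loss | 17.0 | 16.2 | 17.5 | 15.3 |
| Day 91, Control 40% at one year, 10% loss | 11.7 | 11.1 | 12.2 | 10.5 |
| Day 91, Control 48% at one year, 10% loss | 9.7 | 9.2 | 10.1 | 8.7 |
| Day 28, protocol hazards, 10% loss by Day 91 | 6.2 | 6.1 | 6.3 | 6.0 |

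A Kaplan-Meier estimate censored at last known alive has no such bias under these assumptions, because the censoring is independent of outcome.

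**Loss in one arm only.** With 10% uniform loss in one arm and both arms truly at 69.5%, exact enumeration with 75 per arm gives a type I error of 5.3% for unknown = alive, against 4.9% without loss.

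**Illustrative p-values** (chi-square without continuity correction; the splits of unknowns are assumptions):

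| Observed with unknowns counted alive | Unknown | Unknown = alive | Complete case | Unknown = dead |
|---|---|---|---|---|
| 65/75 v 52/75 | 3 ELAD | 0.010 | 0.015 (62/72 v 52/75) | 0.056 (62/75 v 52/75) |
| 65/75 v 52/75 | 3 Control | 0.010 | 0.007 | 0.002 |
| 65/75 v 52/75 | 3 in each arm | 0.010 | 0.010 | 0.016 |
| 61/75 v 52/75 | 2 Control | 0.088 | 0.071 | 0.041 |

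In the first row, if one or two of the three ELAD unknowns had died, p would be 0.019 (64/75) or 0.034 (63/75).

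**The case against.** The strongest reply is that the plan's two versions bracket the truth in every equal-loss scenario above, while unknown = dead is always furthest from it. That stands: unknown = dead is a stress test and not a better estimate. The value of 0.056 also needs all three ELAD unknowns to have died and no Control subject to be unknown. On the protocol hazards, an ELAD subject lost while alive has a chance of 1 − 0.8645/0.9306 = 7% of dying by Day 91, so that result requires strongly informative loss, which the documents neither show nor exclude.

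The follow-up provisions are also good:

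- Protocol 4.4 excludes anyone who refuses the extension or cannot give a home-visit address.
- Protocol 5.5.7 sets weekly home visits. Section 5.5.8 requires repeated calls, registered letters and a record search.
- Protocol 5.5.9 and 10.2 separate stopping treatment from refusing follow-up.
- Protocol 13.2 adds extension contacts, 13.4 allows a vendor search, and SAP 7 commits to tracing each subject.

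Residual unknowns should be few. They are not excluded: Protocol 3 ends site monitoring after full withdrawal, 13.3 carries lost subjects over as lost, and the vendor search is optional.

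A reader might infer more than the documents support:

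- **That the rule favours ELAD.** It does not do so in general. With equal loss it shrinks the difference, and the last row of the p-value table shows it working against ELAD.
- **That SAP 7.1.1 contradicts 7.2.1.** It does not. It is a different estimator, although its Day-91 value can differ from the 7.2.1 proportion.
- **That the unknowns would be hidden.** SAP 4.1 says: "Survival status at time of Day 91, Day 180, Day 365 and time of cut-off will be summarized using ITT populations". The two denominators in 7.2.1 also differ by the number unknown. Day 28 is not in the 4.1 list.
- **That the SAP 7 sentence shows a serious conflict.** It is a wording mismatch, since 7.2.1 states its rule openly. The same sentence also omits the steroid dates in 7.1.4 ("If start dates are partial/missing for steroid use, the following imputation will be followed") and the sensitivity analysis in 7.3.6 ("the analyses will be repeated after the missing data is imputed using the last observation carried forward (LOCF) approach").

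**Conclusion.** The point holds as a minor one. Both planned versions are slightly biased even under benign loss. At 10% uniform loss, unknown = alive understates the Day-91 difference by about 0.5 to 0.8 points and complete case overstates it by about 0.4 to 0.6, across the protocol and SAP survival assumptions. Neither version examines unequal or informative loss, and agreement between them is not evidence that the result withstands it.

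These sizes rest on exponential survival, a hazard ratio of 0.4 and uniform loss. The p-values rest on assumed splits. With no unknown status all versions coincide. The primary log-rank analysis censors at last known status and is unaffected. The documents do not support replacing the chi-square test as lead analysis; that would be a preference.

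**What to change.** In SAP 7.2.1:

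1. Keep the protocol-named chi-square test and both planned counting rules.
2. Add ITT Kaplan-Meier survival at Days 28 and 91 by arm, censored at last known alive, with a Greenwood 95% confidence interval for the difference. The curve is already planned in SAP 7 and 7.1.1.
3. Add one sensitivity row, either unknown = dead or a tipping-point analysis by arm. Kaplan-Meier does not replace this row, because it too is biased if loss is informative.
4. Report the number of unknowns per arm at both days beside the results.

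In SAP 7, list the 7.2.1 counting rule among the exceptions to the no-imputation sentence. The same edit can cover 7.1.4 and 7.3.6.

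The cost is one more table and short text edits. No new data are needed.

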2 STUDY OBJECTIVES

The primary objective of the study is to evaluate safety and efficacy of ELAD[®] with respect to overall survival (OS) of subjects with a clinical diagnosis of alcohol-induced liver decompensation (AILD) through at least Study Day 91, with follow-up Protocol VTL-308E providing additional survival data up to a maximum of 5 years that will be included, as available, through VTL-308 study termination (after the last surviving enrolled subject completes Study Day 91). The primary objective will be assessed using a Kaplan-Meier survival analysis of the Intent-to-Treat (ITT) population utilizing a log-rank test.

The secondary objective is to evaluate the proportion of survivors at Study Day 91 using a chi-squared test.

The exploratory objectives will identify potential differences between treatment groups in factors related to standard demographics, selected baseline characteristics, medical history, and standard of care. These factors will be prespecified in the SAP, and are based on previously-identified and medically-pertinent influences on treatment outcomes in alcoholic liver disease, as well as on factors shown to be important in prior studies of ELAD. In addition, the relationship between outcomes and ELAD System performance, therapeutic interventions of interest and administration of concomitant pharmacotherapies of interest will be assessed in order to help inform product labeling and use. Furthermore, changes in certain biomarkers of interest will also be evaluated.

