7.4 SECONDARY EFFICACY ANALYSES

7.4.1 Proportion of Survivors at Study Day 91

A chi-square test will be used to evaluate the proportion of subjects who survived at End of Study Day 91 based on the ITT population. Two-tailed alpha will be set at 0.05. This analysis will also be carried out on the mITT, PP and Safety populations as sensitivity analyses.

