1.2.2 Secondary Objectives

The secondary objectives are defined as:

- To estimate the effect of ELAD on the proportion of survivors at Study Day 28 and Study Day 91 using a Chi-squared test;
- To estimate the effect of ELAD on the proportion of subjects achieving a 20% reduction in total bilirubin by Day 7 (ECBL20 Yes);

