Appendix D Bleeding Search Terms

Aggravated bleeding tendency
Bleeding tendency
Haemorrhagic diathesis
Hemorrhagic diathesis
Haemorrhage abnormal
Haemorrhagic disorder
Haemorrhagic disorder due to circulating anticoagulants
Hemorrhage abnormal
Hemorrhagic disorder due to circulating anticoagulants
Spontaneous haematoma
Spontaneous hematoma
Spontaneous haemorrhage
Spontaneous hemorrhage
Gastric haemorrhage
Gastric varices haemorrhage
Gastroduodenal haemorrhage
Mallory-Weiss syndrome
Oesophageal haemorrhage
Oesophageal varices haemorrhage
Portal hypertensive gastropathy
Anal haemorrhage
Colonic haematoma
Intestinal haematoma
Large intestinal haemorrhage
Mesenteric haematoma
Mesenteric haemorrhage
Portal hypertensive enteropathy
Rectal haemorrhage
Small intestinal haemorrhage
Chronic gastrointestinal bleeding
Gastrointestinal haemorrhage
Haematemesis
Haematochezia
Intra-abdominal haematoma
Intra-abdominal haemorrhage
Lower gastrointestinal haemorrhage
Melaena
Upper gastrointestinal haemorrhage
Application site haematoma
Application site haemorrhage
Catheter site haematoma
Catheter site haemorrhage
Infusion site haematoma
Infusion site haemorrhage
Injection site haematoma

Injection site haemorrhage
Abnormal withdrawal bleeding
Anovulatory cycle
Bleeding anovulatory
Delayed menarche
Dysfunctional uterine bleeding
Dysmenorrhoea
Early menarche
Menometrorrhagia
Menorrhagia
Menstrual discomfort
Menstrual disorder
Menstruation irregular
Metrorrhagia
Polymenorrhagia
Polymenorrhoea
Premenstrual cramps
Premenstrual dysphoric disorder
Premenstrual headache
Premenstrual pain
Premenstrual syndrome
Retrograde menstruation
Withdrawal bleed
Scrotal haematoma
Testicular haemorrhage
Deep dissecting haematoma
Haemorrhage subcutaneous
Haemorrhage subepidermal
Mucocutaneous haemorrhage
Skin haemorrhage
Subcutaneous haematoma
Arterial haemorrhage
Arterial perforation
Bloody discharge
Exsanguination
Extravasation blood
Haematoma
Haemorrhage
Internal haemorrhage
Shock haemorrhagic
Venous haemorrhage

Signature Page for VV-CLIN-002328 v2.0

| | |
|---------|--|
| Approve | [name] Clinical Operations 24-Aug-2018 21:20:02 GMT+0000 |
|---------|--|

| | |
|---------|--|
| Approve | [name] Executive 25-Aug-2018 07:20:20 GMT+0000 |
|---------|--|

| | |
|---------|--|
| Approve | [name] Medical 26-Aug-2018 02:27:43 GMT+0000 |
|---------|--|

Signature Page for VV-CLIN-002328 v2.0

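### The SAP has three tested secondary endpoints where the protocol has one, and neither document sets a testing order, a gate on the primary result or an alpha split

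*SAP*

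**What the plan says.** Protocol Section 2 names a single secondary objective: "The secondary objective is to evaluate the proportion of survivors at Study Day 91 using a chi-squared test". For that endpoint, in the ITT population, Protocol 7.4.1 adds: "Two-tailed alpha will be set at 0.05".

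SAP 1.2.2 lists more. Its first secondary objective is "To estimate the effect of ELAD on the proportion of survivors at Study Day 28 and Study Day 91 using a Chi-squared test", and its second is the effect on ECBL20. SAP 7.2.2 gives ECBL20 the same rank: "A secondary endpoint for the VTL-308 study will be the proportion of subjects who achieve ECBL20 at Study Day 7 in the ITT population". For the comparison it says: "Differences between treatment groups will be analyzed using a Chi-squared test". SAP 6.1 again assigns chi-squared tests to survival at Days 28 and 91. SAP 7.2.1, covering the same two survival proportions, speaks only of estimation with 95% confidence intervals. It does so for four populations and with two treatments of subjects whose status is unknown.

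The SAP states a significance level for the primary analysis only: under Section 7 the overall survival (OS) hypothesis is "tested at the two-sided 0.05 level of significance". It gives no level for Day 28 or ECBL20. Under SAP 1.1 the SAP overrides the protocol where they conflict. Neither document ranks the secondaries, conditions them on OS or splits alpha. The one conditional rule, in SAP Section 6, concerns further subgroup summaries of OS.

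**The concern.** This is a pivotal trial with a single, well-protected primary test. The error rate of its secondary claims is not controlled by anything in the plan. If OS is missed, nothing says that a nominally significant result on Day-28 survival or bilirubin does not count as a secondary success. If OS is met, three further claims could be made with no joint error limit.

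The first situation is foreseeable from the documents. Protocol Section 1 reports that ITT survival in the predecessor trial, VTI-208, did not differ statistically. SAP 7.2.2 says a post-hoc analysis of that trial's Safety population suggested more ECBL20 responders on ELAD. SAP 7.3.4 reports significant differences there at every bilirubin threshold from 10% to 40%, and treats bilirubin change as a possible surrogate. Protocol 5.4.1.2 meanwhile cautions that extracorporeal therapy itself affects serum bilirubin. A positive bilirubin result beside a negative survival result therefore needs a rule written in advance.

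**Working it through.** **The plan's own figure.** Neither document states an error rate for the secondaries. The nearest figure is the primary power in SAP 1.3. With power = Φ(½√d·|ln HR| − 1.96):

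- 55 deaths, HR 0.417: ½·7.416·0.875 − 1.96 = 1.28, power 0.900.
- 65 deaths, HR 0.447: ½·8.062·0.805 − 1.96 = 1.29, power 0.901.

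Both reproduce the stated 90%. The primary test at two-sided 0.05 is not in question.

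**Inputs for the secondaries**

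- Three chi-squared tests (SAP 1.2.2, 6.1, 7.2.2).
- Two-sided 0.05 each. This is stated for Day 91 (Protocol 7.4.1) and assumed for Day 28 and ECBL20.
- 75 subjects per arm (SAP 1.3).
- Control hazard 0.004 per day and hazard ratio 0.4 (Protocol 7.1), so 0.0016 per day on ELAD.
- Assumed, in neither document: an ECBL20 rate of 40% and its association with survival.

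**Step 1: independence, as an upper reference.** No effect on any endpoint.

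- Either direction: 1 − 0.95³ = 0.143.
- In ELAD's favour: 1 − 0.975³ = 0.073.

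**Step 2: the survival endpoints overlap.** Every death by Day 28 is also a death by Day 91. With exponential survival at 0.004 per day:

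- p28 = 1 − exp(−0.112) = 0.106
- p91 = 1 − exp(−0.364) = 0.305
- correlation = √[p28(1 − p91) / (p91(1 − p28))] = √[(0.106·0.695)/(0.305·0.894)] = 0.52

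From 0.0016 per day up to 0.0077 per day (half dead at 90 days, the rate quoted in Protocol Section 1), the correlation runs from 0.54 down to 0.49.

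**Step 3: chance of at least one false significant secondary.**

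| Model | Either direction | Favouring ELAD |
|---|---|---|
| Independent tests | 14.3% | 7.3% |
| Trivariate normal: survival correlation 0.50–0.55, ECBL20–survival correlation 0–0.5 | 12.4–13.6% | 6.2–6.9% |
| Simulated subjects, 75 per arm | 13.4–13.8% | 6.7–7.0% |
| One test at 0.05 | 5% | 2.5% |

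The subject-level simulation used 100,000 null trials per setting, uncorrected chi-squared tests and exclusion of deaths by Day 7 from ECBL20, as SAP 7.2.2 directs. Hazards were 0.004 and 0.0028 per day, the latter being (0.004 + 0.0016)/2. The death hazard ratio of ECBL20 responders to non-responders was 1, 0.4 or 0.2. At a given hazard, changing that ratio moved the result by about 0.1 percentage point. In the normal model, raising the ECBL20–survival correlation from 0 to 0.5 lowers it by about 1 point.

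**Step 4: after the fix.** With a gate on OS and a fixed sequence, a false claim requires rejecting the first true null hypothesis in the order, which is tested at 0.05. The joint error over OS and the secondaries is therefore at most 0.05 (0.025 in ELAD's favour) for any correlation. For comparison, an equal Bonferroni split tests each secondary at 0.05/3 = 0.0167 and gives 1 − (1 − 0.0167)³ = 0.049 if independent, at the price of a stricter level for Day 91.

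**The case against.** The strongest reply is that the SAP makes no confirmatory secondary claim. It has one primary endpoint, one primary population and one test, and its secondary objectives are phrased as estimation. No text lets a secondary rescue a failed OS result, and the two survival proportions largely re-read the same deaths as OS. What stands is that the primary is protected and that misuse of a secondary is a risk, not a stated intention. The reply does not close the gap: SAP 1.2.2 and 6.1 assign tests to the survival proportions, and 7.2.2 assigns one to ECBL20. If only description is meant, the SAP should say so.

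Four stronger readings are tempting, and the documents support none of them.

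- A reader might take 14% as the chance of a false win for ELAD. It counts false results in either direction, including apparent harm. The figure favouring ELAD is about 6–7%.
- A reader might say that each secondary is specified at 0.05. That level is written for Day 91 alone. For the others it is inferred from chi-squared tests without a level and, for Day 28, from 95% intervals.
- A reader might infer from the approval line "Clinical Operations 24-Aug-2018 21:20:02 GMT+0000", set against a protocol amendment of November 2015, that endpoints were added late or after data were seen. The line dates approval of SAP version 2.0. It does not show when Day 28 or ECBL20 was first included, and the reasons given for ECBL20 are literature and VTI-208.
- A reader might rest the point on the open-label design. Blinding does not control multiplicity, death is objective, bilirubin is a laboratory value, and Protocol 5.5.7 blinds post-discharge investigators and home visitors.

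**Conclusion.** The point holds as a gap in error control for the secondary endpoints and goes no further. One tested secondary became three with no order, gate or allocation. Read at two-sided 0.05 each, with no treatment effect, they carry about a 12–14% chance of at least one false significant result. In ELAD's favour that chance is about 6–7%, more than double the 2.5% of a single test. This rests on applying 0.05 to all three, on exponential survival at or near the protocol's hazards, and on an assumed ECBL20 rate and link to survival. The link matters little, and the rate does not enter the normal approximation. The OS test, its power and its sample size are unaffected, and no inference about the timing or motive of the added endpoints is warranted. It should be corrected because the correction is cheap.

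**What to change.** Add to SAP 7.2:

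- Secondary endpoints are tested confirmatorily only if the primary ITT log-rank test is significant at two-sided 0.05.
- They are then tested in fixed order, each at two-sided 0.05 in the ITT population: Day-91 survival first, as the protocol's endpoint, then the two SAP-added endpoints in a pre-set order (for example Day-28 survival, then ECBL20 as defined in 7.2.2). Confirmatory testing stops at the first non-significant result.
- For both survival steps, one treatment of unknown status is the tested analysis (for example the first rule in 7.2.1, which counts subjects not known to be dead as survivors). The other is a sensitivity analysis.
- All other populations, and all p-values after the stop, are reported as nominal.

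Also align the estimation wording in SAP 1.2.2 and 7.2.1 with the chi-squared tests named in 1.2.2 and 6.1, so that each step has one identifiable test. Record that Day 28 and ECBL20 are SAP additions to the protocol's list.

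The cost is SAP wording. No primary power or sample size is lost. The downside is that a lower-ranked endpoint may be descriptive only, even with a small p-value. The relative rank of Day 28 and ECBL20 is the sponsor's choice, provided it is fixed in advance.
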